12.1 Sample Size and Power

The primary outcome of interest is efficacy of letrozole relative to the placebo, thus the pre- to post-treatment change in a proliferation index (percent of cells expressing Ki-67) is the basis of the power analyses. From our pilot study, the average percentage of cells expressing Ki-67 at baseline was 6.4%, and the average change in percent of cells expressing Ki-67 was a 3.7% reduction, for subjects meeting the same eligibility requirements as will be used in this proposed trial.

A 1:1 randomization of 96 evaluable subjects will provide 90% power to detect an effect size of 0.67 standard deviations with a Type I error rate of 5% using a two-sample, two-sided t-test. In other words, if one assumes a common standard deviation of change of 5.5% (as observed in the pilot study for the 33 subjects matching eligibility criteria for the proposed trial) for both placebo and letrozole groups and if mean change for placebo is zero, then there will be 90% power to detect an average change of 3.7% in Ki-67 in the letrozole group with a Type 1 error rate of 5%. Note that the 3.7% reduction is what was seen in the pilot study. Using a conservative drop-out rate of 10% (it was 2% in the pilot study), enrollment of 108 subjects should provide the required 96 evaluable subjects for the primary endpoint.

12.2 Statistical Analysis

All analyses will be intent-to-treat. All subjects randomized will be evaluable for safety and all subjects that have both a pre and post specimen are evaluable for efficacy. Primary analysis of efficacy will be performed on all evaluable subjects and secondary analysis will be done on those subjects who received at least 3 months of study medication. From our experience we have very little missing data, however, if the missing data rate is above 5%, we will use multiple imputation to impute these values to perform the primary and secondary analyses.

The primary outcome will be change in Ki-67 (percent of cells expressing Ki-67) from baseline to 6 months. The two-sample t-test will be used to compare the change in Ki-67 between the letrozole and placebo groups. Any difference in baseline values of Ki-67 between the two groups would

be due to chance, however, if there is a significant difference, then analysis of covariance adjusting for baseline values will be performed. Due to potential skewness in these variables we will assess whether or not the Central Limit Theorem may be assumed. Given the sample size the existence of an extremely high degree of skewness would require the use of the Wilcoxon Signed Rank test.

For the secondary endpoints, similar methods as above will be used to compare the treatment and control groups at two time points for all markers, i.e., serum hormones, mammographic breast density, and clinical laboratory tests. We will also correlate change in the primary biomarker Ki-67 with change in other markers (e.g., bioavailable estradiol, pS2, GREB-1) using Pearson's correlation coefficient. Again, if there exists a high degree of skewness in these variables, Spearman's correlation will be utilized.

Multiple regression analysis will also be used to investigate whether changes in Ki-67 are due to variables other than treatment effect (e.g., age, cytomorphology, Gail risk; as well as the predictive effect of other biomarkers on modulation of Ki-67). Best subsets and stepwise approaches will be employed while controlling for treatment group.

For comparison of moderate or worse toxicities we will consider grade 3 toxicity or premature trial discontinuation as the critical events. The prevalence of events in the letrozole vs. the placebo arm will be examined by Fisher's exact test.

Evaluation of drug-induced hormonal changes - We will examine whether Letrozole has any effects on serum levels of bioavailable estradiol, and testosterone, determined at baseline and after six months of study medication. We will determine whether addition of letrozole alters the frequency of menopausal symptoms.

Adverse Events and Quality of Life – Change from baseline to six months for hot flash score (Mayo Clinic), fatigue (brief fatigue inventory), overall quality of life (BCPCT), bone turnover markers, HDL/total cholesterol, and C-reactive protein will be compared between the two groups using the two-sample t-test. Similarly, demographic variables (e.g., age, education) and hormonal levels will be tested for use as covariates on each of these endpoints. We will also assess the effects of change in serum hormones (if any) and baseline 25-OH vitamin D levels on incidence and severity of arthralgias and fatigue.

Within Letrozole Comparisons at baseline, 6 and 12 months - On all of our quantitative continuous measures we will perform a repeated measures analysis comparing the 6 and 12 month values to baseline and also with each other. This will give us some preliminary indication whether there is any benefit or detriment of 12 months of treatment. For all the above analyses of exploratory endpoints, as well as for changes in proliferation, results from the 12-month timepoint (following six months of open-label treatment with active agent) will also be analyzed and compared to the baseline and six month values with caution since the double-blind, randomized nature of the comparison is no longer present. However, since

every effort is made to conduct the assessment and quantification of biomarkers without knowledge of treatment arm, the results could be informative.

Since this is a phase IIB trial, the power and sample size for the primary endpoint was determined with a two-sided type I error rate of 5%. All subsequent secondary, tertiary and exploratory analyses will also be tested with a two-sided type I error rate of 5%. This may result in an elevated false positive rate for these secondary and tertiary analyses, however, since this is a Phase IIB study, we felt to control the type I error rate for the secondary, tertiary and exploratory analyses would be too conservative.

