There were no significant changes in cytomorphology, serum estradiol (Figure 4), testosterone, progesterone, SHBG, ER intensity score, or mammographic density although small reductions were seen for Masood score, estradiol, testosterone, and progesterone (see Table 1). There was no change observed in IGF-1. Results for IGF-1 and ER are similar to those reported by Harper-Wynne et al. [Harper-Wynne 2002] for high risk postmenopausal women not taking hormones.

Figure 4: Estradiol Change with Six Months of Letrozole

[figure not shown]
Reported side effects included hot flashes, arthralgias, fatigue and temporary hair thinning. Median change in hot flash score was 0 (-8 to +9). Seventeen percent reported an increase, 14% a decrease, and 69% reported no change in hot flashes over the duration of the study. Thirty-eight percent reported arthralgias and 41% fatigue when questioned on a monthly basis. The regimen was well-tolerated and only one subject discontinued study prematurely (after 4 months). This is in comparison to the ongoing National Cancer Institute of Canada MAP.2 trial of exemestane vs placebo, where 5 of our accrued 32 subjects discontinued study within the first few months primarily due to hot flashes and related symptoms.

We performed a sub-analysis utilizing the 33 subjects whose baseline Ki-67 was $\geq 2\%$ and who were taking estrogen with or without a progestin, i.e., those who meet the eligibility criteria for the proposed Phase II trial. The baseline, post-study, and change values (Table 2) were similar to those of the entire group of 42 subjects.

Variable/Biomarker	Median Values		
	Baseline	Post-Study	Change (relative)
Age, years	49		
5-Year Gail Risk, %	1.9		
Cytomorphology, Masood Score	14	14	-1
Ki-67, %	5.0	1.6	-3.0 (-0.83)
ER, %	41.0	50.0	-7.0 (-0.11)
ER, IS	0.70	0.53	-0.04 (-0.12)
Mammographic Density, % area	32.8	32.6	0.9
Estradiol, pg/ml	59.9	46.7	-7.4
Testosterone, ng/ml	0.60	0.57	-0.07
Progesterone, ng/ml	3.5	2.5	-0.3
SHBG, nM	57.1	51.5	0.3
IGF-1, ng/ml	185	187	6.6
IGFBP-3, ng/ml	4291	4409	81
IGF-1:IGFBP-3 molar ratio	0.16	0.16	0.005

[figure not shown]
Median baseline Ki-67 was 5.0% and median six month Ki-67 was 1.6%. The median absolute change was a reduction of 3.0% (95% CI, -5.6% to -1.7%). The relative change was an 83% reduction (95% CI, -75% to -10%). A decrease in Ki-67 was exhibited by 28 of the 33 subjects (Figure 5). Median change in Masood cytormorphology index was -1 (range -5 to +1).

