6.13 Registration/Randomization/Consent

Potential subjects will be registered for the screening portion of the study by site study coordinator and principal investigator on a site screening log. Potential subjects will be given a unique screening number by the site staff and this will be affixed to all eligibility specimens and documents that will be sent to KUMC for review. No PHI should be attached to these items.

Site staff will not randomize a subject until verification by KUMC Trial Coordinator by means of a faxed request (standard form provided for this purpose which will include an eligibility checklist and notification of acceptable consent) for a particular potential subject. The designated KUMC Trial Coordinator will fax back to the Site Coordinator an approval to randomize the subject based on the review of the eligibility checklist provided by the site.

Approved eligible subjects will be randomized by a randomization schedule at each site, prepared and provided by the Study Statistician. The site staff and subjects will be blinded as to the assignment to drug or matched placebo.

The subject will be assigned a randomization number, after stratification by site and type of hormone replacement therapy. The randomization schedule will be stratified by site (each site will be provided a unique list for use only at that site), and whether the subject is on an estrogen preparation alone, or estrogen plus a progestin preparation. Randomization will be in sequential order according to the randomization list provided. Subjects approved for randomization will be assigned a site specific randomization number, consisting of four digits. The first digit will identify the site (to be determined later) and three digits identifying the specific potential subject.

Sub-contracted sites other than KUMC may use the study consent for the screening RPFNA, or use a research/clinical consent for that purposes. Subjects are not officially on study until they have made it through the entire eligibility process. KUMC will use the High Risk Protocol Consent (KUMC HSC#4601) for the purposes of the screening RPFNA.

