10.1 Ki-67

Breast Cells from RPFNA are pooled in modified cytolyt and sent to KUMC by express mail within 72 hours of RPFNA and all will be processed to slides within 96 hours. Cells are processed to thin prep slides via standard manufacturer's specifications.

A minimum of three slides will be made by a liquid-based cytologic technique: at least one each for cytomorphology, Ki-67 and microdissected prior to RNA extraction. Total epithelial cells will be delineated with Mayer's hematoxylin counterstain and proliferating cells with a MIB-1 antibody for Ki-7. Only baseline slides containing > 500 epithelial cells are processed and stained for Ki-7. Antigen retrieval is performed with 10 nmol/L citrate buffer (pH 6) in a Biocare (Walnut Creek, CA) decloaking chamber for two minutes at 120 degrees C. Slides are then stained with a MIB-1 monoclonal antibody (M7240 Dako Cytomation, Carpinteria, CA) at a 1:20 dilution in a Dako Autostainer [Khan 2005]. Hyperplastic clusters are preferentially assessed and the number of cells with unequivocal nuclear staining out of 500 cells assessed and recorded. Manual counting will be employed and scoring assessed by two laboratory technicians. The scores will consist of number of cells assessed, and number of positive cells for Ki-67. A separate score for each technician and a consensus score will be recorded. The consensus score will be utilized for analysis of the primary endpoint. Representative cell clusters are archived with a digital imaging system.

In the event that fewer than 500 epithelial cells are present in the Ki-67 slide on the follow-up RPFNA, the cytology slide will be destained and used for Ki-67 staining. If there are still less than 500 evaluable cells present when all slide material is combined the post-treatment value for Ki-67 will be considered as the proportion of epithelial cells staining positive for Ki-67 relative to the total number of epithelial cells present. If no staining for Ki-67 is observed and there are less than 500 evaluable cells, the value will be imputed as the reciprocal of the total number of evaluable cells present. If there is no staining and greater than 500 cells, the value will be assumed to be zero. Subjects with less than 100 evaluable cells will be considered not evaluable for Ki-67.

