12.0 STATISTICAL METHODS

The study is a Phase II, double-blind, randomized, placebo-controlled clinical trial to assess the potential efficacy of letrozole as a chemopreventive agent, as measured by changes in proliferation index (Ki-67) between baseline and 6-months. Secondly, the study will evaluate other pharmacodynamic properties of the agent and assess which biomarkers, if any, are modulated. Side effects, adverse events, and quality of life will also be assessed.

Standard randomization strategies will be employed with type of HRT (E vs E+P) as the only stratification factor other than institutional site so that each site can be provided with a unique randomization schedule at initiation. All eligible subjects will be randomly assigned to letrozole or placebo in a 1:1 ratio.

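### Baseline Ki-67 is adjusted for only if a baseline significance test is positive, and the stratification factors enter no named analysis: stated power holds, but precision is given up and most chance imbalance stays in the estimate

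*Combined protocol and SAP*

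**What the plan says.** Section 12.2 compares the change in Ki-67 between arms with a two-sample t-test. It accepts that any baseline difference between randomised arms would be a chance finding, but then provides that "if there is a significant difference, then analysis of covariance adjusting for baseline values will be performed". It states neither the baseline test nor its level, and does not say whether the ANCOVA would replace the t-test or stand beside it.

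A second conditional step follows: an "extremely high degree of skewness would require the use of the Wilcoxon Signed Rank test". No threshold for skewness is given.

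Section 6.13 says: "The subject will be assigned a randomization number, after stratification by site and type of hormone replacement therapy". Section 12.0 agrees: "Standard randomization strategies will be employed with type of HRT (E vs E+P) as the only stratification factor other than institutional site". Neither factor is then named in the primary test, the secondary comparisons, the exploratory regression (which lists age, cytomorphology, Gail risk and other biomarkers as examples) or the safety and quality-of-life analyses. For those last endpoints, demographic variables and "hormonal levels will be tested for use as covariates on each of these endpoints", which again lets the data choose the covariates.

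**The concern.** Under randomisation, a significance test of a baseline difference tests a null hypothesis already known to be true. Its p-value does not show whether baseline is prognostic, which is what makes adjustment worthwhile.

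The documents give reason to expect baseline to matter here:

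- Section 2.8 reports that six of the seven pilot women with baseline Ki-67 below 1.5% had no decrease on letrozole.
- Section 4.3 admits women on a minimum baseline Ki-67, so some regression to the mean is likely. An unadjusted change score fixes the slope of follow-up on baseline at 1.
- Section 2.8 also reports reductions in 27 of 35 women on estrogen alone and 4 of 7 on estrogen plus progestin. The numbers are small, but HRT type was thought important enough to stratify on.

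Three things are at stake: precision that the collected data could provide, an estimate that carries any non-significant chance imbalance, and a primary model that is not fully fixed before the data are seen.

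**Working it through.** **Inputs from Section 12.1.** 96 evaluable women, 48 per arm; two-sided alpha 0.05; SD of change 5.5 points; difference 3.7 points; placebo mean change zero.

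**Assumptions, not in the documents.** Baseline SD, follow-up SD, their correlation (rho), a 5% level for the baseline test, and normal data with a common slope.

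**Step 1: the plan's own figure.** Effect size 3.7/5.5 = 0.673. Noncentral t with 94 df gives power 0.904, so the stated 90% is reproduced. The 95% CI half-width is 1.986 × 5.5 × √(2/48) = 2.23 points.

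**Step 2: ANCOVA on the same women.** With equal SDs, the SD at each visit is s = 5.5/√(2(1 − rho)) and the ANCOVA residual SD is s√(1 − rho²). Power is noncentral t with 93 df.

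**Step 3: the rule as written, read as a switch.** 200,000 simulated trials per rho: test baseline at 5%; if significant use ANCOVA, otherwise the t-test on change. Adjustment was triggered in about 5% of trials.

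| | rho 0.25 | rho 0.5 | rho 0.7 |
|---|---|---|---|
| SD at each visit, s | 4.49 | 5.50 | 7.10 |
| ANCOVA residual SD | 4.35 | 4.76 | 5.07 |
| Power, t-test on change | 0.904 | 0.904 | 0.904 |
| Power, conditional rule | 0.916 | 0.912 | 0.908 |
| Power, ANCOVA always | 0.985 | 0.965 | 0.943 |
| Type I error, conditional rule | 0.039 | 0.043 | 0.045 |
| ANCOVA CI half-width (points) | 1.76 | 1.93 | 2.06 |

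**Step 4: imbalance left in the estimate.** An observed baseline difference D moves the change-score estimate by (1 − slope) × D; with equal SDs the slope is rho. The largest non-significant D is 1.986 × s × √(2/48), and the median absolute D is 0.6745 × s × √(2/48).

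| | rho 0.25 | rho 0.5 | rho 0.7 |
|---|---|---|---|
| D at the edge of significance | 1.82 | 2.23 | 2.88 |
| Shift at that edge | 1.37 | 1.11 | 0.86 |
| As a share of 3.7 | 37% | 30% | 23% |
| Median D | 0.62 | 0.76 | 0.98 |
| Shift at the median | 0.46 | 0.38 | 0.29 |
| As a share of 3.7 | 13% | 10% | 8% |

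If the edge imbalance runs against letrozole, power in that trial is P(Z > (2.23 − (3.7 − shift))/(residual SD × √(2/48))) = 0.55, 0.64 and 0.72. This is a rare case. More commonly, when the baseline p-value lies between 0.05 and 0.20 (about 15% of trials), simulated type I error of the planned t-test is roughly 10%, 9% and 7% at the three correlations, while ANCOVA holds about 5%.

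**Step 5: unequal SDs.** Let follow-up SD be k times baseline SD, with SD of change held at 5.5. Baseline SD is then 5.5/√(1 + k² − 2k·rho), the residual SD is k × baseline SD × √(1 − rho²), and the slope is k·rho.

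- k = 0.75: ANCOVA power 0.998, 0.995 and 0.992.
- k = 1.25: 0.963, 0.932 and 0.909.
- k = 1.25 with rho 0.8: baseline SD 5.5/√0.5625 = 7.33, slope 1.0, residual SD 9.17 × 0.6 = 5.5. Power is 0.903, so there is no gain, and no shift from imbalance either.

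**The case against.** The strongest reply is that no stated property of the plan fails. Section 12.1 sizes the trial for the test that Section 12.2 names, the 90% is real, overall alpha is held, and the estimate is unbiased over randomisations. In a phase II proof-of-principle trial, a more precise alternative is an improvement and not the repair of an error. That is right, and it limits the weight of the point.

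The ANCOVA sentence can also be read as a supplementary analysis. The conditional-rule row above would then not apply, and doubt about the primary model would rest on the skewness clause. But baseline would then never enter the primary test and the precision loss would be complete. Either way the text should say what role ANCOVA has.

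The size rests on assumed correlations and SDs, and Step 5 shows that the gain can vanish. This stands: the text supports the criticism firmly, the size much less so. The data will not be normal either. Section 12.1 reports that "the average percentage of cells expressing Ki-67 at baseline was 6.4" per cent, while Section 2.8 gives, for the 33 matching pilot women, "Median baseline Ki-67 was 5.0% and median six month Ki-67 was 1.6" per cent. The third decimals are therefore illustrative.

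The 0.55 to 0.72 power figures describe an edge case; the typical shift is small. For the strata, omission is usually conservative, the loss cannot be calculated from the documents, and the exploratory regression's covariate list is open-ended. The covariate testing for safety and quality of life does not bear on the primary model.

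**Conclusion.** The concern holds, as a change that should be made and not as a fault that invalidates the trial. The plan keeps its 90% power, but ties baseline adjustment to a test that fires in about one trial in twenty at an assumed 5% level. With equal SDs and rho from 0.25 to 0.7, it forgoes a rise in power from 0.904 to between 0.943 and 0.985, and a CI half-width narrower by 0.2 to 0.5 points (2.23 less 2.06, 1.93 or 1.76). If the SDs differ, the gain may be larger or close to nil. In no scenario examined was ANCOVA materially worse than the t-test. Chance imbalance below the significance threshold stays in the estimate: usually a modest shift, occasionally close to a third of the target difference. The stratification factors should be in the model because they governed the randomisation; no figure can be put on that part.

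**What to change.** Make ANCOVA the unconditional primary analysis: six-month Ki-67 (or change) on treatment, baseline Ki-67, HRT type (E vs E+P) and site, with small sites pooled by a stated rule. Delete the baseline significance test. Keep the unadjusted t-test as a sensitivity analysis.

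Replace the skewness switch with a choice made now. One option is raw-scale ANCOVA as primary, since the 3.7-point target is on that scale, with a rank-based ANCOVA always reported beside it. If a transformed primary analysis is preferred, name the transformation; it must accept zeros, because Section 10.1 provides: "If there is no staining and greater than 500 cells, the value will be assumed to be zero".

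Use the same model for the continuous secondary, safety and quality-of-life endpoints, with covariates named in advance instead of tested for inclusion.

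No extra women, visits or assays are needed: baseline Ki-67 is an entry criterion, and HRT type and site are known at randomisation. The cost is revised wording in Section 12.2 and two decisions before unblinding: the site-pooling rule and the analysis scale. The sample size can stay as it is.

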1.0 Objectives

Our primary hypothesis is that proliferation and expression of other estrogen response genes in hyperplastic breast tissue obtained by RPFNA from high risk women on chronic HRT will be favorably modulated by six months of letrozole relative to placebo without substantially increasing hot flashes or worsening overall quality of life.

To test our hypothesis, we have formulated the following objectives:

- 1.1 To determine whether Ki-67 in hyperplastic foci of breast epithelium obtained by random periareolar fine needle aspiration from postmenopausal high-risk women on HRT is reduced by six months of letrozole.
- 1.2 To determine if letrozole causes an increase in hot flashes, fatigue, pain, stiffness; a deterioration in overall quality of life; as well as deleterious changes in bone turnover markers, total cholesterol:HDL ratio, and C-reactive protein.
- 1.3 To determine if morphologic characteristics as assessed by nuclear morphometric measurements and semiquantitative Masood index score improve with six months of letrozole.
- 1.4 To determine if six months of letrozole in women on a stable dose of hormone replacement results in consistent down modulation of estrogen responsive genes, particularly pS2 and GREB-1.

At the conclusion of this proof of principle study, we will have established a firm clinical and biological basis for a large randomized study of letrozole versus placebo in high-risk postmenopausal women requiring hormone replacement for symptom control with development of breast cancer as an endpoint. If aromatase inhibitor treatment is found to reduce risk of breast cancer in women receiving hormone replacement, it would provide middle age women with tools to alleviate perimenopausal symptoms while minimizing breast cancer risk.

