normal, non-proliferative breast tissue, Ki-67 is expressed in approximately 0.2%-0.7% of cells in the terminal lobular duct unit but has been reported in 1-6% of cells in proliferative breast disease [Shaaban 2002, Pavelic 1992, Allred 1998]. Shaaban et al. in a correlational cross-sectional study have reported that high Ki-67 in foci of hyperplasia (median 3.8%) is associated with a greater risk of breast cancer than those with low Ki-67 (median 0.8%) [Shaaban 2002]. We have observed a median Ki-67 labeling index of 1% in RPFNA samples from high-risk postmenopausal women exhibiting hyperplasia without atypia and a median Ki-67 of 2.8% in RPFNA samples containing hyperplasia with atypia [Khan 2005]. A number of antihormonal treatments effective in breast cancer treatment and/or prevention have been shown to reduce proliferation indices in benign and cancerous breast epithelial cells by 17-50% relative to baseline [Clarke 1993, Fernando 1994, Chang 2000, Dowsett 2000, Dowsett 2001, Dowsett 2005A, Decensi 2003]. Estrogen withdrawal has been directly correlated with a 5-fold reduction in Ki-67 in MCF-7 xenografts [Detre 1999]. Reduction in proliferation (Ki-67) at two weeks and 12 weeks in the neoadjuvant IMPACT Trial (tamoxifen, anastrozole, combination) was positively associated with disease free survival [Dowsett 2005A]. Tamoxifen has been shown to reduce proliferation (Ki-67) in benign breast tissue of postmenopausal women [de Lima 2003]. For predictive value, Ki-67 must be reduced by at least 35-50% by the intervention [Urruticoechea 2005].

At the present time, change in proliferation as measured by Ki-67 is probably the most commonly used primary response indicator used in moderately sized proof-of-principal Phase I and II breast chemoprevention trials in high risk postmenopausal women [Fabian 2005A].

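### The rank-test fallback for skewed Ki-67 change is a one-sample or paired test, so as written it cannot compare letrozole with placebo

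*Combined protocol and SAP*

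**What the plan says.** The hypothesis in Section 1.0 is comparative: proliferation "will be favorably modulated by six months of letrozole relative to placebo". Section 12.2 makes change in Ki-67 from baseline to 6 months the primary outcome and sets the test: "The two-sample t-test will be used to compare the change in Ki-67 between the letrozole and placebo groups". It then undertakes to check for skewness and names the fallback: "Given the sample size the existence of an extremely high degree of skewness would require the use of the Wilcoxon Signed Rank test".

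The next paragraph says that for the secondary markers (serum hormones, mammographic density, clinical laboratory tests) "similar methods as above will be used to compare the treatment and control groups at two time points". The paragraph on adverse events and quality of life states its own method: those endpoints, including bone turnover, lipids and C-reactive protein, "will be compared between the two groups using the two-sample t-test". Within-arm change has a separate paragraph, headed "Within Letrozole Comparisons at baseline, 6 and 12 months", which uses a repeated measures analysis.

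The sentence on the fallback is the only mention of a Wilcoxon test in the document. Sections 3.0 and 12.1 name only the two-sample t-test.

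**The concern.** Allocation is 1:1, stratified by site and type of hormone therapy but not matched (Sections 6.13 and 12.0), so no between-arm pairs exist. A signed-rank test can therefore only ask whether change from baseline is centred on zero, in one arm or in the pooled sample. It cannot ask whether letrozole differs from placebo.

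If skewness is judged extreme, the analyst must either depart from the written plan or run a test that does not answer the primary question. The plan gives no numerical criterion for extreme skewness, which widens the discretion.

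A fall shared by both arms is plausible. Entry requires Ki-67 of at least 1.5% (Section 4.3), and a group selected for a high first reading tends to read lower the second time without treatment. A within-arm test would credit that fall to the drug.

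**Working it through.** **1. The plan's own figure.** Section 12.1 gives a difference of 3.7 points, an SD of change of 5.5 ("if one assumes a common standard deviation of change of 5.5"), two-sided 5% and 90% power.
- Effect size: 3.7 / 5.5 = 0.673.
- Exact two-sample t-test: 47.4 per arm, so 48 per arm or 96 in total. Power at 48 per arm is 90.4%.
- Dropout of 10%: 96 / 0.9 = 106.7, or 54 per arm = 108.

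The sample size reproduces. It rests on the t-test, so the fallback does not disturb it.

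**2. Can the fallback be reached?** In the pilot subgroup of 33, mean baseline Ki-67 was 6.4% (Section 12.1) against a median of 5.0% (Section 2.8). Mean change was -3.7 against a median of -3.0. Both gaps point to skewness. Suppose letrozole lowers Ki-67 by a constant proportion, 3.7 / 6.4 = 58%. Under the simulation model in step 4, the typical sample skewness of change in the letrozole arm is then -1.4 to -1.9. With no drug effect, population skewness of change is only 0.0 to 0.2, although single samples vary widely.

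**3. Simple case: an assumed shared fall.** Normal change scores, SD 5.5, 48 per arm, no drug effect, 10,000 trials. The signed-rank test is run within the letrozole arm, which is an assumption. The standard error of the arm mean is 5.5 / √48 = 0.794.

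| Shared fall (points) | Fall / SE | Signed-rank | Exact one-sample t | Rank-sum between arms |
|---|---|---|---|---|
| 0.5 | 0.63 | 9.0% | 9.5% | 4.7% |
| 1 | 1.26 | 22.9% | 23.5% | 5.5% |
| 2 | 2.52 | 66.7% | 69.4% | 5.0% |

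**4. Shared fall produced by the entry rule.** Log-normal Ki-67, 500 cells counted, entry at 1.5% or more, 48 per arm, no drug effect. The log SDs (between women, visit to visit) are assumptions chosen to give an SD of change near 5.5.

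| Screening median | Log SDs | SD of change | Signed-rank | Rank-sum |
|---|---|---|---|---|
| 2.0% (assumed) | 0.8, 0.62 | 5.51 | 30.3% | 4.6% |
| 2.8% | 0.8, 0.51 | 5.49 | 13.9% | 5.4% |
| 4.6%, fits pilot baseline | 0.5, 0.5 | 5.38 | 6.4% | 5.2% |
| 4.3%, fits pilot baseline | 0.6, 0.5 | 5.67 | 6.8% | 4.8% |

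The first two rows use 5,000 trials each and the last two 2,500 each. The shared mean fall is 0.58 points in the first row and 0.34 in the second. The 2.8% comes from Section 2.5, which reports "a median Ki-67 of 2.8% in RPFNA samples containing hyperplasia with atypia". With a between-woman log SD of 0.7, the first two signed-rank rates become 37.8% and 16.7%, and rank-sum is 4.7% in both.

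**5. Does the right fallback keep the power?** With 48 per arm, normal changes, SD 5.5 and a true difference of 3.7, simulated power is 88.7% for rank-sum and 90.6% for the t-test. Its efficiency relative to the t-test for normal data is 3/π = 0.955, so 90% power would need 94.8 / 0.955 = 99.3, about 100 evaluable subjects.

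**The case against.** The strongest reply is that the intention is plain. Sections 3.0, 12.1 and 12.2 all describe a two-group comparison, and within-letrozole change has its own paragraph. A statistician would very likely read the sentence as rank-sum, and the wording could be amended before database lock. This stands as a reason to call the error a probable slip. It does not make the sentence correct: this is the written rule for the primary endpoint, and the correction should precede sight of the data.

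A second reply is that the false-positive rates describe a within-arm analysis that the plan does not state, and ignore the trigger. Normal scores would hardly ever count as extremely skewed. With an assumed trigger of pooled sample skewness above 2 in absolute value, the share of null trials that both trigger and reject is about 7% for the 2.0% median, 3% for the 2.8% median and 1% for the pilot-matched cases. With a trigger of 1, it is about 15%, 7% and 2-3%. This stands: the rates in steps 3 and 4 apply once the fallback is used, not to the trial overall.

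Third, the larger rates do not match the planning data. After entry selection, the 2.0% and 2.8% cases give baseline means of 5.0% and 5.7%, against 6.4% in the pilot. The 2.8% figure is for samples with atypia, whereas entry accepts hyperplasia with or without it. This also stands, and the pilot-matched excess over 5% is small.

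Finally, how far the cross-reference to similar methods carries the fallback is open to some argument, since clinical laboratory tests could be read to include lipids and C-reactive protein. The adverse-event paragraph, however, states a two-sample t-test for those endpoints.

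**Conclusion.** The concern holds and should be fixed. The named fallback has no between-arm contrast, and nothing else in the document corrects it. It affects the primary endpoint and the markers that Section 12.2 analyses by similar methods. It does not affect the default t-test, the sample size, or the endpoints given their own two-sample t-test.

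That the test does not fit the comparison follows from the text alone. The size of the harm is illustrative: it assumes that the fallback is invoked, that it is run within the letrozole arm, and a particular pattern of untreated change. On those assumptions the false-positive rate runs from near nominal (6-7%) to about 30% under the entry rule, and to 67% for an assumed shared fall of 2 points.

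**What to change.** In Section 12.2, replace the signed-rank test with the two-sample Wilcoxon rank-sum (Mann-Whitney) test of change in Ki-67 between the letrozole and placebo groups. State that the same fallback applies to the markers covered by similar methods in the following paragraph. Stratifying by the randomisation factors is optional.

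The cost is one sentence, with no extra data and no extra patients. The 96 evaluable subjects still give close to 90% power under normal changes. Make the change before unblinding.
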